5.2 Study Procedures

5.2.1 Pre-study Procedures

Pre-study procedures must take place no more than 14 days prior to the first dose of decitabine except where noted below.

1. Bone marrow aspirate and biopsy. Standard bone marrow procurement procedures will be followed for collection of the tissue. Assessments performed on bone marrow will include correlative studies (collected under HRPO# 201011766), morphologic assessment, cytogenetics, and FISH.
2. Bone marrow or peripheral blood for flow cytometry
3. Skin biopsy sample (collected under HRPO# 201011766). There is no required time frame for this sample; it may have been collected months or even years prior to the first dose of decitabine.

5.2.2 Baseline Evaluation

Baseline evaluations must take place no more than 7 days prior to the first dose of decitabine.

1. Medical history
2. Physical exam including height, weight, and ECOG performance score.
3. Record transfusion requirements for 8 weeks before first dose of study drug
4. CBC with differential and platelets
5. Serum chemistries, including bicarbonate, calcium, glucose, total protein, albumin, BUN, potassium, chloride, sodium, creatinine, total bilirubin, AST, ALT, alkaline phosphatase, LDH
6. Urine β HCG pregnancy test if appropriate

5.2.3 Day 1 of Each Cycle

1. Physical exam, including weight
2. CBC with differential and platelets
3. Serum chemistries, including bicarbonate, calcium, glucose, total protein, albumin, BUN, potassium, chloride, sodium, creatinine, total bilirubin, AST, ALT, alkaline phosphatase, LDH

5.2.4 Cycle 1 Days 1-10

Decitabine administration, 20 mg/m² per day given as a 1-hour continuous intravenous infusion. The dose will be calculated based on actual patient weight at the beginning of each cycle. Patients may be premedicated with lorazepam, prochlorperazine, palonosetron, or ondansetron at the treating physician's discretion.

5.2.5 Cycle 1 Day 4 \pm 1

Obtain 3 mL peripheral blood for correlative studies. Sample must be obtained 45 minutes \pm 15 minutes after beginning the infusion, before the decitabine infusion

is complete, and should be obtained from the opposite arm as the infusion. The sample should be collected in a 3 mL K3EDTA tube pre-loaded with 8 mcL of tetrahydrouridine (THU 500 mcg/mL), an inhibitor of cytidine deaminase. The sample should be processed by the Tissue Procurement Core Facility at the Siteman Cancer Center. Plasma should be separated and stored per protocols.

5.2.6 Cycle 1 Day 10 ± 1

Bone marrow aspirate and biopsy. Standard bone marrow procurement procedures will be followed for collection of the tissue. Assessments performed on bone marrow will include correlative studies (collected under HRPO# 201011766), morphologic assessment, cytogenetics, and FISH.

5.2.7 Weekly

CBC with differential and platelets. After the first cycle, this may be changed to every other week at the discretion of the treating physician.

5.2.8 Every Other Week

Serum chemistries, including bicarbonate, calcium, glucose, total protein, albumin, BUN, potassium, chloride, sodium, creatinine, total bilirubin, AST, ALT, alkaline phosphatase, LDH. After the first cycle, this may be changed to every month at the discretion of the treating physician.

5.2.9 Cycles 1, 2, 4 and 6 Day 28 ± 4 days

Bone marrow aspirate and biopsy. Standard bone marrow procurement procedures will be followed for collection of the tissue. Assessments performed on bone marrow will include: correlative studies (collected under HRPO# 201011766), morphologic assessment, cytogenetics, and FISH.

Patients who achieve with clinical response (CRi or better) and are receiving cycles every 6 weeks, will undergo bone marrow biopsies on day 42 ± 4.

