Patients with progressive disease after two cycles (defined as a clear increase in bone marrow blast count, typically a > 50% increase in bone marrow blasts over baseline) should be removed from study.

Patients with stable disease may continue on study and should undergo a diagnostic bone marrow biopsy at the end of even numbered cycles.

Once AML patients achieve morphologic complete remission with incomplete blood count recovery (CRi) or MDS patients achieve a marrow complete response (Marrow CR) as defined in Section 9.0, decitabine administration may be decreased to 20 mg/m²/day for ten consecutive days every 6 weeks, to limit myelosuppressive toxicity and improve count recovery. After 2 cycles at 6 week intervals, the dose may be reduce to 20 mg/m²/day for five consecutive days in 6 week cycles, at the discretion of the treating physician. After two cycles of five consecutive days of treatment, if the patient meets the definition of CR with complete cytogenetic response as defined in Section 9.0, administration may further be decreased to three consecutive days per cycle at the discretion of the treating physician.

Sample collection for correlative studies:

Bone marrow biopsies should be performed at baseline, at Cycle 1 Day 10 ± 1, and at Day 28 ± 4 of Cycles 1, 2, 4, and 6. Following Cycle 6, bone marrow biopsies should be performed at the discretion of the treating physician to assess for relapse or progression.

Peripheral blood samples should be collected on Day 4± 1 of Cycle 1. Collection should be obtained 45 ± 15 minutes after decitabine infusion is initiated.

Genomic Predictors of Decitabine Response in AML/MDS

Table of Contents

Section	Page
Section 4.21.0 INTRODUCTION	7
1.1 Rationale.....	7
1.2 Decitabine and Hypomethylating agents in AML/MDS.....	9
1.2.1 Pharmacokinetics and Metabolism of Decitabine.....	11
1.2.2 Experience with extended dosing schedules.....	12
1.3 Correlative Studies	13
2.0 OBJECTIVES.....	15
2.1 Primary Objective.....	15
2.2 Secondary Objectives	15
3.0 PATIENT SELECTION.....	16
3.1 Inclusion Criteria	16
3.2 Exclusion Criteria.....	16
3.3 Inclusion of Women and Minorities.....	17
4.0 REGISTRATION PROCEDURES	18
4.1 Confirmation of Patient Eligibility.....	18
4.2 Patient Registration in the Siteman Cancer Center Database.....	18
4.3 Assignment of UPN.....	18
5.0 INVESTIGATIONAL PLAN	20
5.1 Summary of Study Design.....	20
5.2 Study Procedures	20
5.2.1 Pre-study Procedures.....	20
5.2.2 Baseline Evaluation.....	21

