6.3 Modification in Dose or Schedule for Treatment Response

Once AML patients achieve morphologic complete remission with incomplete blood count recovery (CRi) or MDS patients achieve a marrow complete response (Marrow CR) as defined in Section 9.0, decitabine administration may be decreased to 20 mg/m²/day for ten consecutive days, and the cycles may be administered every 6 weeks to limit myelosuppressive toxicity, at the discretion of the treating physician. After two cycles at six week intervals, the dose may be reduced to 20 mg/m²/day for five consecutive days of treatment in six week intervals. If the patient meets the definition of CR with complete cytogenetic response as defined in Section 9.0, administration may further be decreased to three consecutive days per cycle at the discretion of the treating physician.

[Redacted]

[Redacted]

[Redacted]

[Redacted]

[Redacted]

[Redacted]

[Redacted]

[Redacted]

[Redacted]

[Redacted]

[Redacted]

[REDACTED]

[REDACTED]

[REDACTED]

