14.2.3 Secondary Endpoint Analyses

The overall response rate (CR/CRi/PR) and complete response rate (CR/CRi) will be compared with historical controls[2], and the 95% confidence intervals will be provided.

The rate of patient specific mutation clearance after 10, 28, and 56 days of therapy will be determined using an Illumina based platform. We will compare the rate of mutation clearance between the patients who achieve a CR/CRi after 4 cycles and those who do not. We anticipate that we will identify between 6 and 25 exonic SNVs per case (the range obtained with >200 AML samples sequenced to date with whole genome or exome sequencing), and that the expected 95% confidence

interval of the mean variant allele frequency will be $\pm 2.56\%$ and $\pm 1.25\%$, respectively, if we assume an anticipated standard deviation of 3.2% within the same clone. The change of tumor burden over time and its association with clinical response will be assessed using 2-way ANOVA for repeated measurement data, followed by the ad-hoc multiple comparisons for between-group differences (e.g., responders vs. non-responders) at given time points as well as the between-time differences within each group. The resultant critical P values will also be corrected using permutation analysis for multiple testing.

The steady-state plasma decitabine concentration on day 4 ± 1 will be measured and correlated with clinical overall response.

The percent decrease in bone marrow methylcytosine will be calculated on day 10 ± 1 . We will compare this reduction with previously published data and between the patients who achieve CR/CRi and those who do not. The correlation of peak plasma levels of decitabine with response will be assessed using 2-sample t-test or Mann-Whitney non-parametric rank-sum test as appropriate. The change of total bone marrow DNA methylcytosine from baseline and its association with both steady-state plasma drug levels and response will be assessed using 2-way ANOVA for repeated measurement data, followed by the ad-hoc multiple comparisons for between-group differences (e.g., responders vs. non-responders) and between-time differences. Similar analyses will be performed for the correlation of expression profiles and SNP analysis with pharmacokinetic data.

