Appendix 2 Study Flow Chart

Study Flow Chart

Test	Pre-study ¹	Base-line ²	All Cycles Day 1	All Cycles Days 1-10 ³	Cycle 1 Day 4 ± 1	Cycle 1 Day 10 ± 1 and 28 ± 4	Every week	Every 2 weeks	Even cycles Day 28±4	End of Study
Informed Consent	X									
Medical History		X								
Physical Exam		X ^a	X ^b							X
Transfusion Requirements ^c		X ^c	Ongoing							
Bone Marrow Aspirate and Biopsy	X ^d					X ^d			X ^d	X ^d
Flow Cytometry ^c	X									
Peripheral blood for correlative studies					X					
Pregnancy test		X								
CBC with differential and platelets		X	X				X ^f			X
Serum Chemistries ^g		X	X					X ^f		X
Decitabine administration ^h				X						
Adverse Events			Ongoing							
Post-study follow-up										X ⁱ

¹ To be performed within 14 days of the first dose of decitabine.

² To be performed within 7 days of the first dose of decitabine.

³ Decitabine may be reduced to Days 1-5 or Days 1-3. See Section 6.3 for details.

^a To include height, weight, and ECOG.

^b To include weight.

^c Care should be given to record the frequency of transfusions from 8 weeks prior to first dose of study drug through the duration of the study.

^d Bone marrow biopsy and aspirate should be performed at baseline, at Cycle 1 Day 10 ± 1, and at Day 28 ± 4 of Cycles 1, 2, 4 and 6 for clinical disease assessment. Patients who achieve with clinical response (CRi or better) and are receiving cycles every 6 weeks, will undergo bone marrow biopsies on day 42 ± 4. Following Cycle 6, bone marrow biopsies should be performed at the discretion of the treating physician to assess for relapse or progression. Standard bone marrow procurement procedures will be followed for collection of the tissue. To include: correlative studies (collected under HRPO# 201011766), morphologic assessment, cytogenetics and FISH at all time points. A skin biopsy sample (collected under HRPO# 201011766) is required at pre-study, but may have been collected months or even years prior to first dose of decitabine.

^e On bone marrow or peripheral blood.

^f After Cycle 1, these labs may be obtained every other week (CBC) or once a month (Chemistries) at the discretion of the treating physician.

^g Serum chemistries include bicarbonate, calcium, glucose, total protein, albumin, BUN, potassium, chloride, sodium, creatinine, total bilirubin, AST, ALT, alkaline phosphatase, and LDH.

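### Under Sections 6.3 and 5.2.9 an early responder's Cycle 2 marrow can fall at about study day 70, while Section 14.2.3 compares clearance by response at a nominal day 56

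*Combined protocol and SAP*

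**What the plan says.** The point concerns the version with its statistics in Section 14.0, the only one in the part of the file shown that has a 6-week option. The other part is not shown and may hold a later version.

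- **Trigger.** Section 6.3 applies once an AML patient reaches CRi or an MDS patient reaches Marrow CR, and then "the cycles may be administered every 6 weeks to limit myelosuppressive toxicity, at the discretion of the treating physician". The Study Schema describes the same step as "ten consecutive days every 6 weeks, to limit myelosuppressive toxicity and improve count recovery". Neither sets a minimum number of cycles. The first scheduled response marrow (Section 9.3) is Cycle 1 Day 28 ± 4.
- **Marrow day.** Section 5.2.9 states that patients with CRi or better who "are receiving cycles every 6 weeks, will undergo bone marrow biopsies on day 42 ± 4". Appendix 2 note d repeats this and adds what each marrow carries: "To include: correlative studies (collected under HRPO# 201011766), morphologic assessment, cytogenetics and FISH at all time points".
- **Conflicting schedule.** Sections 1.3 and 8.0 still set the Cycle 2 correlative marrow at Day 28 ± 4, with no exception for 6-week cycles.
- **Analysis.** Section 14.2.3: "The rate of patient specific mutation clearance after 10, 28, and 56 days of therapy will be determined". Then: "We will compare the rate of mutation clearance between the patients who achieve a CR/CRi after 4 cycles and those who do not". And: "The change of tumor burden over time and its association with clinical response will be assessed using 2-way ANOVA for repeated measurement data", followed by responder against non-responder comparisons at each time point. It does not say whether time means the nominal or the actual sampling day.

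**The concern.** The event that permits late sampling is remission, and remission also defines the groups. Remission at Cycle 1 and CR/CRi after 4 cycles are not the same thing, but they are closely linked. If more CR/CRi patients than others have their Cycle 2 marrow two weeks late, a contrast labelled day 56 partly compares day 70 with day 56. An ANOVA with time as a category cannot separate the two.

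At stake is the secondary objective in Section 2.2 that relates velocity and depth of mutation clearance to response. If variant allele frequency (VAF) keeps falling between days 56 and 70, the contrast flatters responders. If the clone regrows in the longer off-drug interval, the error runs the other way.

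**Working it through.** **1. The plan's own day.** Inputs: 28-day cycles (Section 5.1) and a Cycle 2 marrow on Day 28 ± 4. Then 28 + 28 = 56, as in Section 14.2.3, with a window of 52 to 60.

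**2. The day under Section 5.2.9.** With Cycle 1 on schedule and Cycle 2 run as a 6-week cycle, 28 + 42 = 70, with a window of 66 to 74. The two windows do not overlap.

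**3. Who moves.**
- A patient in CRi at the Cycle 1 marrow can move.
- A patient who first remits at Cycle 2 or later keeps day 56.
- An MDS patient in Marrow CR may go to 6-week cycles under Section 6.3. Section 5.2.9 moves the marrow only for CRi or better, and Marrow CR is by definition not CR (Section 9.2), so this patient does not clearly belong on either side.
- Patients in either group can be late after holds for infection (6.1), organ dysfunction or grade 3-4 toxicity (6.2). Only a delay above 8 weeks between cycles ends participation (6.0).

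**4. Effect on a rate, if nominal days were the divisor.** Write V0 for baseline VAF and Vt for VAF on day t. The true log rate is ln(V0/Vt)/t, and the nominal one is ln(V0/Vt)/56. Their ratio is t/56:
- day 70: 70/56 = 1.25
- day 66: 66/56 = 1.18
- day 74: 74/56 = 1.32

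Section 1.3 defines velocity as a natural log rate and names no divisor, so this error is possible but not prescribed.

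**5. Effect on the day-56 contrast (illustration only).** Assume equal true clearance in both groups, exponential decline with half-life h, and late samples exactly 14 days late. Let d be the share of CR/CRi patients who are late minus the share of others who are late. The false ratio of geometric mean VAF (CR/CRi over others) is 2^(−14d/h). Group sizes of 45 and 55 are those in the power paragraph of Section 14.2.3.

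| Late, CR/CRi | Late, others | d | h = 14 | h = 28 | h = 56 |
|---|---|---|---|---|---|
| 0/45 | 0/55 | 0 | 1.00 | 1.00 | 1.00 |
| 11/45 | 11/55 | 0.044 | 0.97 | 0.98 | 0.99 |
| 22/45 | 11/55 | 0.289 | 0.82 | 0.90 | 0.95 |
| 22/45 | 0/55 | 0.489 | 0.71 | 0.84 | 0.92 |
| 22/45 | 27/55 | −0.002 | 1.00 | 1.00 | 1.00 |

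The documents give neither half-life nor late counts. The 22 is an assumed ceiling, about half of 45. An earlier protocol version (Section 1.2.2) reports that, in the cited 10-day decitabine study, 50% of eventual complete responders had low marrow blasts after one cycle. Low blasts are not CRi as defined here, and the ceiling also assumes that every such patient is switched. The range is 0 to 22.

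**6. Against the plan's stated precision.** Section 14.2.3 gives the error of a patient's mean VAF "if we assume an anticipated standard deviation of 3.2% within the same clone". This reproduces: 1.96 × 3.2/√6 = 2.56 points and 1.96 × 3.2/√25 = 1.25 points. A 14-day shift is VAF × (1 − 2^(−14/h)). It exceeds 2.56 points only if day-56 VAF is above 5.1%, 8.7% or 16.1% for h = 14, 28 or 56. Below that, one patient's shift lies within the stated error, although a systematic shift would not average out across a group.

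**The case against.** The strongest reply is that the protocol contradicts itself on the sampling day. Section 5.1 refers the reader to Section 8.0 for the correlative studies, and Sections 8.0 and 1.3 keep Cycle 2 Day 28 ± 4 without exception. A site could follow them and draw at day 56. This stands: the day-70 sample follows only if Section 5.2.9 and note d, the more specific rule, prevail. If sites differ in their reading, sampling days become mixed and actual dates are still needed.

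Next, the option may not operate at Cycle 2 at all. Section 6.1 gives four cycles without adjustment for cytopenia, Section 5.1 has no 6-week option, and the stated purpose of the longer cycle is to limit myelosuppression. The trigger in 6.3 is response, not cytopenia, so 6.1 does not plainly bar it, but that reading is open. Uptake is discretionary and may be nil.

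Finally, both samples are end-of-Cycle-2 marrows, after the same two 10-day courses if no dose is missed, and Section 1.3 indexes them by cycle. A cycle-aligned comparison is defensible and deserves to be kept, though it answers a different question from clearance by day 56.

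A reader might infer that the plan builds in a 25% error, or that only responders can be sampled late. The documents support neither: no divisor is prescribed, and toxicity or infection holds can delay non-responders too.

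**Conclusion.** The point holds as a minor one. Under Section 5.2.9 a remission-triggered sample at about day 70 can enter a comparison by remission at nominal day 56, and the stated ANOVA has no means of separating the two.

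The size cannot be determined from the documents. It is zero if no physician uses the option, if 6.1 is read to bar it during the first four cycles, or if delays are equal in both groups. The false VAF ratios above depend on assumed half-lives and late counts and are not predictions. It would go too far to infer a bias in favour of responders, since regrowth off drug would reverse it, or to infer damage to the main results. Day 10, Cycle 1 Day 28, the primary objective and the response endpoints are unaffected. Whether a later version in the part not shown already resolves this is unknown.

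**What to change.** In Section 14.2.3:
- Compute clearance velocity from actual days since first dose.
- Analyse the clearance time course with actual sampling day as the time variable in place of nominal-day categories, for example with a simple mixed model of log VAF on actual day and a stated rule for undetectable VAF. A more elaborate model need not be required: there are four samples per patient, and a late patient has none between days 28 and 70.
- Keep the cycle-aligned comparison at the end of Cycle 2 as a sensitivity analysis.

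Align Sections 1.3 and 8.0 with 5.2.9, so that the Cycle 2 correlative day is the same wherever it is stated.

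The cost is wording and slightly more analysis. The Study Calendar Form (Section 15.0) already records the date of each time point, so no marrow or visit is added. The downside is an assumed shape for VAF between samples: the day-56 value of a patient sampled at day 70 is interpolated.

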5.2.10 End-of-Study Procedures

1. Physical exam
2. CBC with differential and platelets.
3. Serum chemistries including bicarbonate, calcium, glucose, total protein, albumin, BUN, potassium, chloride, sodium, creatinine, total bilirubin, AST, ALT, alkaline phosphatase, and LDH.
4. Bone marrow aspirate and biopsy. Standard bone marrow procurement procedures will be followed for collection of the tissue. Assessments performed on bone marrow will include morphologic assessment, cytogenetics, and FISH.

5.2.11 Post-study Follow-up

Patients are to be followed according to standard patient care procedures for 30 days following the date of the last decitabine dose to monitor for toxicity, survival, and response. Thereafter, the investigator or designee will record information on subsequent therapy, disease progression, and/or death every 6 months for 2 years after last dose of study drug or until the patient is lost to follow-up or dies.

5.3 Duration of Therapy

If at any time the constraints of this protocol are considered to be detrimental to the patient's health and/or the patient no longer wishes to continue protocol therapy, the protocol therapy should be discontinued and the reason(s) for discontinuation documented in the case report forms.

In the absence of treatment delays due to adverse events, treatment may continue indefinitely or until one of the following criteria applies:

- Documented and confirmed disease progression
- Death
- Adverse event(s) that, in the judgment of the investigator, may cause severe or permanent harm or which rule out continuation of study drug
- General or specific changes in the patient's condition render the patient unacceptable for further treatment in the judgment of the investigator
- Suspected pregnancy
- Serious non-compliance with the study protocol
- Lost to follow-up
- Patient withdraws consent
- Investigator removes the patient from study
- The Siteman Cancer Center decides to close the study

Patients who prematurely discontinue treatment for any reason will be followed as indicated in the study calendar.

5.4 Concomitant Therapy and Supportive Care Guidelines

5.4.1 Chemotherapy

Patients cannot receive any chemotherapy within 21 days of study enrollment and must have recovered from any treatment-related toxicities. However, patients may be receiving hydrea at enrollment and may continue on hydrea through Cycle 2 of decitabine. An indication for hydrea following 2 cycles of decitabine is evidence that the patient is not responding and decitabine should be discontinued. Other than decitabine, patients cannot receive chemotherapy during this trial.

